#### 10 STATISTICAL CONSIDERATIONS

#### 10.1 STATISTICAL HYPOTHESIS

Moxetumomab pasudotox-tdfk may be combined with rituximab/Ruxience safely in participants with relapsed/refractory HCL.

- Primary Endpoint(s): To determine the safety and toxicity of moxetumomab pasudotoxtdfk and rituximab/Ruxience treated at the planned dose level, in participants with HCL and HCLv.
- Secondary Endpoints:
  - To determine the minimal residual disease (MRD)-free CR rate of the study drug combination is higher than that achieved with 40-50 mcg/kg dose levels of Moxetumomab pasudotox-tdfk alone.
  - o To determine response rate and duration of response.

#### 10.2 SAMPLE SIZE DETERMINATION

- The initial sample size determination: Up to 10 participants are intended to be treated in the trial using the following plan; if a different dose of moxetumomab pasudotox-tdfk is required, up to 16 participants will be needed to be enrolled.
  - Initially, 3 participants will be treated with moxetumomab pasudotox-tdfk 30 mcg/kg and rituximab 375 mg/m^2. If 0/3 have a DLT, then the next 3 participants will be treated with moxetumomab pasudotox-tdfk 40 mg/kg and rituximab 375 mg/m^2.

If 1/3 initial participants treated with 30 mcg/kg have a DLT, then 3 more will be treated at 30 mcg/kg. If no more than 1 of the first 6 have a DLT, then 4 more participants will be enrolled at 30 mcg/kg provided that no more than a total of 2 of the 10 have a DLT with the exception

Version Date: 04/16/2025

of the types noted. The upper one-sided 90% confidence bound on 2/10 is 45.0%. if a 3rd participant has a DLT, accrual will end as soon as this is noted.

If participants are accrued to the 40mcg/kg level, if 0/3 or 1/3 have a DLT (with the exception of the types noted), then 3 more will be treated using those dose levels. If no more than 1 of the first 6 have a DLT, then 4 more participants will be enrolled provided that no more than 2 total of the 10 have a DLT. The upper one-sided 90% confidence bound on 2/10 is 45.0%. if a 3rd participant has a DLT, accrual will end as soon as this is noted.

If 2 of the first 3 participants, or 2 of the first 6 participants, treated with moxetumomab pasudotox-tdfk 40 mcg/kg and rituximab 375 mg/m² have a DLT, then 3 additional participants will be treated with moxetumomab pasudotox-tdfk 30 mcg/kg and rituximab 375 mg/m². If 0/3 or 1/3 of these next 3 have a DLT with these dose levels, then 4 more participants will be enrolled at the 30 mcg/kg level provided that no more than 2 total of the 10 have a DLT with the exception of the types noted. If 2 participants in the first 6 have a DLT at this level, then the trial will end accrual. Furthermore, at any time in the 10 participants, if a 3rd participant has a DLT, accrual will also end as soon as this is noted. The upper one-sided 90% confidence bound on 2/10 is 45.0%.

• Sample size determination for amendment dated 9/21/2021: As of July 2021, a total of 12 participants were enrolled without DLT up to that point, making it likely that 3 participants will be enrolled with moxetumomab pasudotox-tdfk 30 mcg/kg and rituximab 375 mg/m², and 10 with moxetumomab pasudotox-tdfk 40 mcg/kg and rituximab 375 mg/m². Of the first 9 participants so far evaluated for response, 7 (78%) achieved CR, all MRD-free.

Given the encouraging safety and efficacy data from the phase 1 trial, it is desirable to increase the number of participants to gain more experience with moxetumomab pasudotox-tdfkand rituximab and be able to determine whether the efficacy of the combination at 30-40 mcg/kg of moxetumomab pasudotox-tdfk is better than our historical experience of 40-50 mcg/kg of moxetumomab pasudotox-tdfk alone tested for MRD at NIH. Historically, 30 of 64 evaluable phase 1-3 participants treated with moxetumomab pasudotox-tdfk alone achieved MRD-free CR assessed by bone marrow aspirate flow.

To enable additional participants to be enrolled affordably, starting with participant 14, participants will receive the biosimilar Ruxience instead of rituximab. Moxe-R thus represents the combination of moxetumomab pasudotox-tdfk with either rituximab or Ruxience.

If we are being conservative, the 7 of 9 participants who achieved MRD-free CR to date on Moxe-R would need to be considered an interim evaluation and its successful result would be the basis for deciding to add more participants. As such, it would be statistically appropriate to aim for a 0.025 one-sided test between 30/64 and the participants on the current trial. With a total of 26 evaluable participants on Moxe-R and 64 prior participants, a Fisher's exact test with a one sided 2.5% significance level will have 79.8% power to detect a difference between 80% MRD-free CR rate on the present trial and 47% from the 30/64 participants in the prior trials.

While a total of 26 evaluable participants will be enrolled, the accrual ceiling will be set at 30 to include screen failures and inevaluable participants.

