A phase 3 pivotal multicenter single-arm trial (NCT01829711) was designed for relapsed/refractory HCL patients with ≥2 prior systemic therapies including ≥1 prior purine analog. Patients received moxetumomab pasudotox-tdfk 40 mcg/kg intravenously on days 1, 3, and 5 of each 28-day cycle for 6 cycles, or until MRD-negative CR, disease progression, initiation of alternate therapy, or unacceptable toxicity. Disease response and immunohistochemistry MRD status were determined by blinded independent central review. The primary endpoint was durable CR, which required achieving CR and maintaining hematologic remission (HR) for >180 days). HR was defined as hemoglobin >11.0 g/dL, absolute neutrophil count >1.5/nL, and platelet count ≥100/nL without transfusions or growth factors within the preceding 4 weeks of assessments. Eighty patients (63 males, 17 females; median age 60 years (range 34-84) were enrolled. The median number of previous systemic therapies was 3 (2–11); 48.8% of patients were purine analog refractory and 37.5% were unfit for purine analog retreatment. The median number of treatment cycles administered was 6 (1-7). As of May 24, 2017, the durable CR rate was 30.0%, 24/80 patients; 95% confidence interval (CI): 20.3, 41.3). CR rate was 41.3% (33/80 patients; 95% CI: 30.4, 52.8), and ORR was 75% (95% CI: 64.1, 84.0). Among 33 patients who achieved a CR, 27 (81.8%) also achieved MRD negativity. Median time to OR was 5.7 months (95% CI: 5.7, 5.9). Sixty-four patients (80%) achieved hematologic remission. The median duration of hematologic remission from CR, median duration of response, and PFS were not reached.

Of 64 patients treated on the phase 1 (NCT01087333) and 3 (NCT01829711) trials at NIH with 40-50 mcg/kg dose levels of moxetumomab pasudotox-tdfk and evaluated for MRD by bone marrow aspirate flow cytometry, the 30 (47%) of 64 achieved MRD-free CR.

The most frequently reported adverse events (AEs) occurring in >40% of subjects overall were hypoalbuminemia (71.4%), increased ALT (67.3%); increased AST (63.3%), lymphopenia (59.2%), myalgia (57.1%); decreased white blood cell count (51.0%); pyrexia (49.0%); peripheral edema (44.9%); and hypertriglyceridemia (40.8%).

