## 10.4.3 Analysis of the Secondary Endpoint(s)

- Response rates, MRD-free rates, and response durations will be reported descriptively, and the latter will be determined using Kaplan Meier Analyses.
- The MRD-free CR rates will be compared between evaluable participants on this trial and the 30 of 64 evaluable phase 1-3 participants who achieved MRD-free CR from moxetumomab pasudotox-tdfk using a Fisher's exact test, taking the interim results from this trial into consideration.
- The change from rituximab to Ruxience is not expected to result in a change to the CD20 Mab, and the comparison between participants 1-13 treated with moxetumomab pasudotox-tdfk rituximab and participants 14-26 treated with moxetumomab pasudotox-tdfk Ruxience will have limited power to detect a difference between rituximab and Ruxience in HCL. After enrollment of 26 participants, if the difference in MRD-free CR rate from moxetumomab pasudotox-tdfk rituximab vs moxetumomab pasudotox-tdfk Ruxience results is p>0.30 or higher, the results from the 2 groups will be considered close enough to be pooled and the full 26 participants could be compared against the 64 from the moxetumomab pasudotox-tdfk monotherapy studies.

Version Date: 04/16/2025

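### The 79.8% power in 10.2 treats the historical control as 64 newly drawn patients; against the fixed 30/64 that will be used, the test needs 19 of 26 and has 86.9% power at a true 80%

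*Combined protocol and SAP*

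**What the plan says.** The amendment part of 10.2 chooses the level and the comparator together: "it would be statistically appropriate to aim for a 0.025 one-sided test between 30/64 and the participants on the current trial". It then gives the sample sizes ("With a total of 26 evaluable participants on Moxe-R and 64 prior participants") and says that a Fisher's exact test at the one-sided 2.5% level "will have 79.8% power to detect a difference between 80% MRD-free CR rate on the present trial and 47% from the 30/64 participants".

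The comparator is past data wherever it appears. Section 10.2 reports it as history: "Historically, 30 of 64 evaluable phase 1-3 participants treated with moxetumomab pasudotox-tdfk alone achieved MRD-free CR assessed by bone marrow aspirate flow". Section 1.2.1 gives the same result: "the 30 (47%) of 64 achieved MRD-free CR". Section 10.4.3 plans the final comparison with "the 30 of 64 evaluable phase 1-3 participants who achieved MRD-free CR from moxetumomab pasudotox-tdfk using a Fisher's exact test".

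Neither section gives the number of MRD-free CRs needed for significance, or says that the 79.8% treats the control count as random. Section 10.4.3 says the interim results will be taken into account but does not repeat the 0.025 level. It also makes use of all 26 conditional on a comparison of participants 1-13 with participants 14-26 giving p > 0.30.

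**The concern.** No control patients will be enrolled. Once 30/64 is fixed, the only random quantity is the number of MRD-free CRs among the trial's own participants, and the Fisher test reduces to one integer cut-off. A power figure that lets the control count vary is not the probability that this comparison succeeds.

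Two things are at stake. First, 79.8% is the only quantitative support given for 26 evaluable participants, and it describes a different experiment from the one in 10.4.3. Second, the decision rule is left implicit. A result of 18/26 would miss the 2.5% level but fall below a conventional 5%. Because 10.4.3 does not restate the level, a reader of that section alone could not tell how to classify it.

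**Working it through.** **Inputs.** One-sided Fisher's exact test at 0.025; n = 26 on the trial and 64 historical; alternative 80%; control rate 47%; observed control 30/64 = 46.9% (10.2, with 1.2.1 and 10.4.3 agreeing on 30/64). Interim result 7 MRD-free CRs among 9 evaluated (10.2). Pooling rule p > 0.30 (10.4.3).

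**Step 1: reproduce the plan's figure.** Let X ~ Bin(26, 0.80) and Y ~ Bin(64, 0.47). Given X = x and Y = y, the one-sided Fisher p-value is P(H ≥ x), where H is hypergeometric with 90 patients in total, x + y responders and 26 drawn. Summing P(X = x)·P(Y = y) over all pairs with p ≤ 0.025 gives **79.81%**, which matches the stated 79.8%. Close variants do not match:

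| Calculation | Power |
|---|---|
| Random control, rate 0.47, one-sided 0.025 Fisher | 79.8% |
| Random control, rate exactly 30/64 | 80.1% |
| Two-sided 0.05 Fisher, rate 0.47 | 81.3% |
| Pooled normal approximation | 85.0% |

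So the stated figure comes from 64 newly drawn controls at 47%.

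**Step 2: fix the control at y = 30 and find the cut-off.**

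| MRD-free CRs of 26 | Rate | One-sided Fisher p vs 30/64 | P(X ≥ x) at true 80% |
|---|---|---|---|
| 17 | 65.4% | 0.0863 | 97.7% |
| 18 | 69.2% | 0.0442 | 94.1% |
| **19** | **73.1%** | **0.0202** | **86.9%** |
| 20 | 76.9% | 0.0081 | 74.7% |

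The test is significant if and only if X ≥ 19. Power = P(X ≥ 19 | 26, 0.80) = **86.9%**, and 86.9 − 79.8 = 7.1 points above the stated value. With the control fixed, power of about 80% is already reached at a true rate of about 78% (P(X ≥ 19 | 26, 0.78) = 80.4%).

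**Step 3: condition on the interim data.** With 7/9 in hand, at least 19 − 7 = 12 of the remaining 26 − 9 = 17 are needed. P(at least 12 of 17 | 0.80) = 89.4%.

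**Step 4: allow for the pooling condition.** Section 10.4.3 does not name the test behind p > 0.30. Assume a two-sided Fisher test of 13 vs 13, with both groups at a true 80%. Then P(pooling allowed) = 89.0%, and P(pooling allowed and at least 19 of 26) = 78.1%.

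**Step 5: chance of significance with no improvement.** This depends on the true monotherapy rate, which 30/64 only estimates. For assumed true rates, P(X ≥ 19 | 26, p) is:

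| Assumed true rate | 47% | 50% | 55% | 60% |
|---|---|---|---|---|
| P(X ≥ 19) | 0.6% | 1.4% | 4.7% | 12.2% |

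**The case against.** The strongest reply is that nothing has been miscalculated. Section 10.2 describes a two-sample Fisher test, 26 against 64, and 79.8% is the correct unconditional power of that test. The test itself treats the 64 as a sample with error, and averaging over the control when computing power keeps that error in view. This stands in part. The arithmetic is right for its own model, and 79.8% may be kept if it is labelled. But the protocol does not say that this is what the figure represents, and the count entering the planned test is already known.

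A second reply is that the pooling condition brings the overall chance of a pooled success to about 78%, close to the stated figure. That is a fair reason not to print 86.9% without the condition. The closeness is coincidental, however: the 79.8% calculation contains no pooling step.

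A third reply is that the cut-off can be derived from what is stated. That is true for the test in 10.2, but the level is missing from 10.4.3, where the analysis is specified.

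Three stronger readings are tempting and are not supported:

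- **That the trial is underpowered or 26 is too few.** The discrepancy runs the other way: power against the fixed control is higher than stated.
- **That the true one-sided error is 0.6% rather than 2.5%.** The 2.5% is a nominal significance level, and 0.6% holds only if the true monotherapy rate is about 47%. Step 5 shows the chance rising above 2.5% at higher assumed rates.
- **That the Safety Monitoring Committee needs the cut-off.** Section 7.4.2 directs its reviews to unexpected safety issues and gives it no efficacy role.

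**Conclusion.** The point holds as one about what the power figure describes. The 79.8% is the power of a design with 64 random controls at 47%. For the comparison actually planned, against the observed 30/64, the rule is at least 19 of 26 and power at a true 80% is 86.9%, about 7 points higher.

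These figures assume that all 26 are evaluable and pooled, and the 86.9% does not use the 7/9 already seen. Fixing the control changes the power calculation but does not remove uncertainty about the true historical rate. The practical weight is modest: the error is conservative, sample size, test and level are unchanged, and MRD-free CR is a secondary endpoint beside a primary safety endpoint. It is still worth correcting, because the plan relies on the figure and the decision rule is nowhere written down.

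**What to change.** 1. In 10.2, replace the power sentence with: *With the control fixed at 30/64, and if all 26 evaluable participants are pooled under 10.4.3, the one-sided 2.5% Fisher test is significant if at least 19 of 26 achieve MRD-free CR; power is 86.9% if the true rate is 80%.*
2. Either delete 79.8% or keep it labelled as unconditional power with the control count treated as random.
3. In 10.4.3, repeat the one-sided 0.025 level and the 19/26 cut-off.
4. Note that the pooling condition lowers the overall chance of a pooled success (about 78% under the assumption in Step 4; name the pooling test so that the figure can be confirmed), and that conditioning on 30/64 leaves the true monotherapy rate uncertain. If a false-positive chance is quoted, give the range in Step 5 with its assumed rates rather than 0.6% alone.

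The cost is a few sentences. No extra participants, data or analyses are needed.

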#### 10.3 POPULATIONS FOR ANALYSES

#### 10.3.1 Evaluable for toxicity

All participants will be evaluable for toxicity from the time of their first treatment

#### **10.3.2** Evaluable for objective response:

Only those participants who have measurable disease present at baseline, have received at least one cycle of therapy, and have had their disease re-evaluated will be considered evaluable for response. These participants will have their response classified according to the definitions stated below. (Note: Participants who exhibit objective disease progression prior to the end of cycle 1 will also be considered evaluable.)

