#### 2 ELIGIBILITY ASSESSMENT AND ENROLLMENT

#### 2.1 ELIGIBILITY CRITERIA

#### 2.1.1 Inclusion Criteria

- 2.1.1.1 Diagnosis of HCL or HCLv.
- 2.1.1.2 Treatment required for either 1) Absolute neutrophil count (ANC) <1/nL, 2) Hemoglobin <10g/dL, 3) Platelets<100/nL, 4) symptomatic splenomegaly, or 5) enlarging HCL mass > 2cm in short axis. Participants who have eligible blood counts within 4 weeks from the initiation of study will not be considered ineligible if subsequent blood counts prior to enrollment fluctuate and become ineligible up until the time of enrollment.
- 2.1.1.3 Participants must be Pseudomonas-immunotoxin naïve.
- 2.1.1.4 HCL or HCLv with at least 1 prior purine analog, and, for HCL participants with ≥2-years 1 month response, at least 1 other therapy.
- 2.1.1.5 Age ≥18 years as the disease under study, HCL/HCLv, has not been reported in children < age 18.
- 2.1.1.6 ECOG performance status ≤2 (Karnofsky ≥60%, see **Appendix A: Performance Status** Criteria).
- 2.1.1.7 Participants must have adequate organ and marrow function as defined below:
  - Total bilirubin ≤ 1.5 mg/dL, unless consistent with Gilbert's (ratio between total and direct bilirubin > 5)
  - AST and ALT  $\leq$  3x upper limit of normal (ULN)
  - Alkaline phosphatase < 2.5 ULN
  - Serum creatinine  $\leq 1.5 \text{ mg/dL}$  or creatinine clearance  $\geq 60 \text{ mL/min}$  by Cockcroft-Gault equation, where creatinine clearance = (140 -age)(kg weight)/(72 x Creatinine)
  - Serum albumin > 2 g/dL
  - Partial thromboplastin time (PTT) or Prothrombin time (PT)/International Normalized Ratio < 2.5x ULN (If on warfarin, PT/INR < 3.5x ULN; If on any other anticoagulation, Prothrombin time (PT) < 2.5x baseline)
  - Fibrinogen  $\geq 0.5$  lower limit of normal
- 2.1.1.8 The effects of moxetumomab pasudotox-tdfk and rituximab/Ruxience on the developing human fetus are unknown therefore participants must use effective methods of contraception as directed below.

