## 6.4.2 Complete remission (CR)

All of the following:

- Absolute neutrophil count (ANC)  $\geq 1500/\text{mm}^3$
- Platelets  $\geq 100,000/\text{mm}^3$

Version Date: 04/16/2025

- Hgb  $\geq$  11 g/dL
- Regression of splenomegaly on physical exam or by imaging studies.
- Lymph nodes  $\leq 2$  cm by short axis, unless larger lymph nodes not due to HCL
- Absence of hairy cells on BM aspirate smears and H/E stain of the BM biopsy negative for HCL. If the negative BM is before 4 weeks off of growth factors or transfusions, the CR will begin after the 4 week time point once the normal blood counts are consistent with CR.
- CR with MRD in the BMBx by IHC is defined as CR and a ratio of CD20+ cells to T cells of at least 1, and most of the CD20+ cells consistent with HCL.
- CR with MRD in the peripheral blood is defined as CR and a positive peripheral blood FACS or PCR. Suspicious flow is considered positive per protocol.
- Participants meeting all criteria for CR except minimum levels of ANC, platelets and Hgb will be considered CR if MRD is absent by BMBx IHC and by flow cytometry of blood and bone marrow.

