## **10.3.3 Evaluable Non-Target Disease Response:**

Participants who have lesions present at baseline that are evaluable but do not meet the definitions of measurable disease, have received at least one cycle of therapy, and have had their disease reevaluated will be considered evaluable for non-target disease. The response assessment is based on the presence, absence, or unequivocal progression of the lesions.

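### The response-evaluable set is written for solid tumours and contradicts the rest of the plan, and its one-cycle and re-evaluation conditions can raise the tested MRD-free CR rate

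*Combined protocol and SAP*

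**What the plan says.** Section 10.3.2 makes evaluable for response "Only those participants who have measurable disease present at baseline, have received at least one cycle of therapy, and have had their disease re-evaluated". One exception follows: "Participants who exhibit objective disease progression prior to the end of cycle 1 will also be considered evaluable". The section points to response definitions further down, but none follow; the response criteria are in section 6.4. Section 10.3.3 adds a second set: "Participants who have lesions present at baseline that are evaluable but do not meet the definitions of measurable disease". It too requires one cycle and a re-evaluation, and it is not linked to MRD-free CR.

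Other sections describe the disease differently. The first three of the five entry routes in section 2.1.1.2 are cytopenias: "Treatment required for either 1) Absolute neutrophil count (ANC) <1/nL, 2) Hemoglobin <10g/dL, 3) Platelets<100/nL". A mass is only one of the five. CR in section 6.4.2 rests on counts, spleen, nodes and marrow, including "Absence of hairy cells on BM aspirate smears and H/E stain of the BM biopsy negative for HCL".

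The formal efficacy test in section 10.4.3 compares evaluable participants with 30 of 64 evaluable historical patients. It does not cite section 10.3.2. The same section says that, if the two antibody groups are close enough to pool, the full 26 could be compared with the 64. Section 10.2 plans 26 evaluable participants, and "the accrual ceiling will be set at 30 to include screen failures and inevaluable participants". No all-treated efficacy analysis is planned.

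**The concern.** There are two separate problems.

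**Fit.** A participant who enters on a cytopenia with marrow disease only has no lesion to measure. Read literally, that participant is not evaluable under section 10.3.2, and section 10.3.3 does not help because it needs a lesion at baseline. The plan cannot both apply that rule and expect 26 evaluable participants within 30 places. Without a definition, whoever performs the analysis has to decide who counts, possibly with outcomes in view.

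**Selection after treatment starts.** The other two conditions depend on what happens on study. A participant who is never re-evaluated cannot be documented as an MRD-free CR, and one who stops within cycle 1 for toxicity or withdrawal is very unlikely to be one. Dropping such participants raises the tested rate. They can also be replaced, because the ceiling of 30 makes room for inevaluable participants.

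At stake is the comparison that section 10.2 gives as a reason for enlarging the trial to 26.

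**Working it through.** **Inputs.** 26 evaluable participants, 80% against 47% (30/64), Fisher's exact test, one-sided 2.5%, ceiling 30 (section 10.2). The number of treated participants dropped, d, is not given. I take d = 0 to 4, since 30 − 26 = 4. Screen failures share those four places.

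**The plan's own figure.** The plan states that "a Fisher's exact test with a one sided 2.5% significance level will have 79.8% power". Summing over both binomials (26 at 0.80, 64 at 0.47) all outcomes with one-sided Fisher p ≤ 0.025 gives 79.81%. The figure reproduces.

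**Restoring dropped participants as failures.** For x MRD-free CRs among n, p = P(H ≥ x), where H is hypergeometric with n draws from n + 64 patients, of whom x + 30 are MRD-free CRs. The smallest significant count in 26 is 19 (18/26 gives p = 0.044).

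| d restored | n | 19 responders | p | 21 responders | p |
|---|---|---|---|---|---|
| 0 | 26 | 73.1% | 0.020 | 80.8% | 0.003 |
| 1 | 27 | 70.4% | 0.033 | 77.8% | 0.006 |
| 2 | 28 | 67.9% | 0.051 | 75.0% | 0.011 |
| 3 | 29 | 65.5% | 0.074 | 72.4% | 0.018 |
| 4 | 30 | 63.3% | 0.102 | 70.0% | 0.029 |

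At the boundary, one restored participant changes the conclusion. Near the planned 80%, it takes four.

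**False success with no true effect.** If the true rate among all treated is 0.47 and the d dropped are all non-responders, the rate among the evaluable is 0.47 × (26 + d)/26. With 30/64 fixed, success means at least 19 of 26. The last column lets the historical count vary as binomial(64, 0.47).

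| d | Rate among evaluable | P(success), 30/64 fixed | P(success), historical count varies |
|---|---|---|---|
| 0 | 0.470 | 0.6% | 1.5% |
| 1 | 0.488 | 1.1% | 2.2% |
| 2 | 0.506 | 1.7% | 3.2% |
| 3 | 0.524 | 2.6% | 4.5% |
| 4 | 0.542 | 4.0% | 6.1% |

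The nominal 2.5% is passed from d = 3 with 30/64 fixed, and from d = 2 if the historical count varies. Modelling responders instead as binomial(26 + d, 30/64), with the historical count varying, gives 7.2% at d = 4.

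**Direction of the measurable-disease clause.** This is a baseline condition, so it can move the rate either way. If four participants excluded by it were all responders, 21/26 (80.8%) would become 25/30 (83.3%): the clause would have lowered the rate.

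**Recounting the comparator too.** The historical losses are not given. If two were added as non-responders (an assumption), 19/27 against 30/66 gives p = 0.024 and 21/30 against 30/66 gives p = 0.021. Both are significant again.

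**The case against.** The strongest reply has four parts.

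- **The comparator is selected in a similar way.** Section 1.2.1 describes the 64 as patients treated at NIH who were evaluated for MRD by marrow aspirate flow. Part of the bias may therefore cancel, and a modest recount of the historical group could offset the losses in this trial. This stands. A reader might infer that it does not cancel, because section 1.2.1 reports 33 patients treated at 50 mcg/kg and 32 evaluated for MRD. Those figures cover only phase 1 patients at one dose level, while the 64 pool phase 1 and phase 3 patients treated at NIH at 40–50 mcg/kg. They cannot be extended to the 64.
- **Not all early failures are dropped.** Objective progression before the end of cycle 1 stays in the denominator. This stands; what is lost is toxicity, withdrawal and missed re-evaluation.
- **The number dropped may be small or zero.** Under section 3.1.2, failure to complete cycle 1 because of toxicity is a DLT, and the first 12 participants had none (section 3.1.4). Restaging is scheduled, and section 3.6 asks for a safety visit before removal from study. This stands as a reason to expect few losses. It says nothing about later participants, withdrawal or missed re-evaluation. Section 10.2 reports 9 of the 12 evaluated for response; the other 3 may simply have been pending.
- **The endpoint is secondary** in a non-randomized phase 1 trial, and the safety set already includes everyone treated. This limits the severity. It does not justify an undefined denominator for the only formal efficacy test.

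**Conclusion.** The wording defect is established. Section 10.3.2 uses an undefined solid-tumour condition that conflicts with the entry criteria, the response criteria and the plan's own count of 26. A reader might infer that typical hairy cell participants will in fact be excluded, or that this clause inflates the rate. The documents support neither: the planned 26 evaluable within a ceiling of 30 suggests the clause is not meant literally, and its effect has no fixed direction.

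The upward pressure comes from the one-cycle and re-evaluation conditions, and its size is conditional. It is zero if nobody is dropped. With one to four dropped it can overturn a boundary result, but a result near 80% changes only at four. False success runs from 0.6% to 4.0% with 30/64 fixed, or from 1.5% to 6.1% if the historical count varies. These figures assume that every dropped participant is a non-responder, which is certain only for those never re-evaluated, and that the comparator is not recounted. With the historical all-treated denominator unknown, so is the net bias.

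This should be fixed, but it does not threaten the primary safety objective.

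**What to change.** 1. Delete the measurable-disease condition from section 10.3.2 and remove the lesion-based set in section 10.3.3.
2. Define the efficacy set for MRD-free CR as all participants who received any dose of either study drug. Classify response by section 6.4, and count a missing response or marrow assessment as not MRD-free CR.
3. Name this set in section 10.4.3 as the denominator for the comparison with the historical group.
4. State how many patients were treated at NIH at 40–50 mcg/kg in the two earlier trials, and count them by the same rule.
5. Keep the evaluable-only comparison with 30/64 as a sensitivity analysis, and report how many treated participants it leaves out and why.

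The cost is SAP wording and a recount of the historical denominator; no new participant data are needed. The reported rate may be lower, and power falls if anyone is restored. If the 80% holds only among the evaluable and the comparator stays at 64 patients and 47%, an all-treated analysis has 62.9% power with two restored (0.80 × 26/28 = 74.3%) and 45.5% with four (0.80 × 26/30 = 69.3%), against 79.8% with none.
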